To compare the neuromuscular electrical activity (RMS) and muscle fatigue (Hurst index) of the masseter muscles in three groups of patients with different treatments for TMD (GA = Transcutaneous electrostimulation and splint, GB = Percutaneous electrostimulation and splint, and GC = Occlusal splint.) through 6 electromyographic records scheduled weekly in patients from the Physiology Laboratory of the Division of Graduate Studies and Research (DEPeI) UNAM, admitted during the period from August to December 2020.

Specific objectives

- o Register the sociodemographic and clinical variables (age, sex, TMD, BMI, systemic diseases, use of prostheses, number of teeth present, drug intake) prior to TMD treatment in patients admitted to the DEPeI UNAM Physiology Laboratory during the period from August to December 2020.
- o Record the neuromuscular electrical activity (RMS) and muscle fatigue (Hurst Index) of the masseter muscles of the three groups of patients with different treatments for TMD (GA = Transcutaneous electrostimulation and splint, GB = Percutaneous electrostimulation and splint, and GC = Occlusal

splint) by means of 6 electromyographic recordings scheduled weekly (T0 = Basal, T1 = 7 days, T2 = 14 days, T3 = 21 days, T4 = 28 days, T5 = 35 days, T6 = 42 days) in patients from the Laboratory Physiology of the DEPeI, UNAM, admitted during the period from August to December 2020.

o Record TMD signs and symptoms (muscle pain, joint pain, mouth opening limitation, presence of joint sounds and heart rate) during TMD treatments through 6 weekly scheduled evaluations (T0 = Baseline, T1 = 7 days, T2 = 14 days, T3 = 21 days, T4 = 28 days, T5 = 35 days, T6 = 42 days) in patients from the Physiology Laboratory of DEPeI, UNAM, admitted during the period from August to December 2020.

o Identify the changes in neuromuscular electrical activity (RMS) and muscle fatigue (Hurst Index) of the masseter muscles in each group (GA = Transcutaneous electrostimulation and splint, GB = percutaneous electrostimulation and splint, and CG = Occlusal splint) during the TMD treatment (T0 = Baseline, T1 = 7 days, T2 = 14 days, T3 = 21 days, T4 = 28 days, T5 = 35 days, T6 = 42 days) in patients from the Physiology Laboratory of DEPeI, UNAM, admitted during the period from August to December 2020.

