percutaneous electrostimulation and splint, and GC = Occlusal splint) during treatment of TMD according to the sociodemographic and clinical variables (age, sex, TMD, BMI, systemic diseases, use of prostheses, number of teeth present, drug intake), in patients of the Physiology Laboratory of DEPeI, UNAM, admitted during the period from August to December 2020.

Hypothesis

Ha1: There will be a greater decrease in neuromuscular electrical activity (RMS) and muscle fatigue (Hurst index) of the masseter muscles in the treatment group with percutaneous electrostimulation (GB = percutaneous electrostimulation and splint) compared to the values of the electrostimulation groups transcutaneous (GA = transcutaneous electrostimulation and splint) and the control group (CG = Occlusal splint) of patients from the Physiology Laboratory of the Division of Postgraduate Studies and Research (DEPeI), UNAM, admitted during the period from August to December 2020 .

Ho1: There will be no decrease in neuromuscular electrical activity (RMS) and muscle fatigue (Hurst index) of the masseter muscles in the treatment group with percutaneous electrostimulation (GB = percutaneous electrostimulation and splint) compared to the values of the electrostimulation groups transcutaneous (GA = transcutaneous electrostimulation and splint) and the control group (CG = Occlusal splint) of patients from the Physiology Laboratory of the Division of Graduate Studies and Research (DEPeI) UNAM, admitted during the period from August to December 2020.

Material and methods

Type of study

Randomized clinical trial

Study population

Patients with TMD who will enter the Physiology Laboratory of the Division of Graduate Studies and Research (DEPeI) UNAM, during the period from August to December 2020.

The DEPeI UNAM Physiology Laboratory attends approximately 900 patients per year, of which 168 first-time patients are referred from other specialty clinics at DEPeI UNAM. Around 100 appointments are scheduled per month, most of them are for treatment controls through occlusal splint adjustment and electromyographic records. The patients received by the Physiology Laboratory are referred by the Reception and Diagnosis Clinic (Postgraduate), the specialty clinics of the DEPeI, stomatological services of hospitals and private clinics, among others.

Selection and sample size

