The treatment for TMD will be carried out by means of the conventional treatment with an occlusal splint and as an auxiliary method, transcutaneous and percutaneous electrostimulation therapies will be applied by the same operator during the period from August 2020 to June 2021. The appointments for clinical control for signs and symptoms of TMD, splint adjustment, electromyographic records and application of electrostimulation therapy as an adjunct to the use of splint, will be scheduled once a week in the Physiology Laboratory from 9:00 am to 1:00 pm and from 2:00 pm to 6:00 pm: 00pm for six consecutive weeks.

• **Electromyographic recording technique**

The registration system (hardware and software) that will be used for the electromyographic evaluation is the Electromyograph 1.2 UNAM-CINVESTAV, which consists of a two-channel system for the analysis of the electromyographic signal that offers greater precision and facilitates muscle assessment through the estimation made by the software of the RMS for its acronym in English (Root Mean Square) and Hurts Index. (53)

The RMS and Hurts Index will be recorded using three electrodes: one placed at the muscular origin, another at the insertion, and finally one in the behind-the-ear area as a ground or neutral electrode. The RMS recording is performed at maximum intercuspation for 30 seconds; the action potential that is expressed in electrical energy will be recorded in microvolts per second ($\mu\text{V} / \text{s}$).

6 electromyographic recordings will be performed on each patient (one record each week) during the time of splint use. Electromyographic recordings will be scheduled as well as follow-up control appointments, to make adjustments to the physiological occlusal splint.

Occlusal splint fabrication technique

The occlusal splints for the treatment of TMD will be the same for all the participants, they will be made by the Principal Investigator in the Physiology Laboratory of DEPeI, UNAM. The indications for the use of a splint and hygiene will be the same in all patients (the splint is worn 24 hours a day, it is

removed for eating and brushing teeth). The splint is washed with neutral liquid hand soap, no brushing or scrubbing).

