o A descriptive analysis of the main clinical characteristics of the population studied will be carried out in the case of continuous variables, the mean and standard deviation or the median and its interquartile range will be reported according to its distribution normal and antagonistic as n and percentage (%).

o The muscle effect of electrostimulation therapies within and between groups over time (before and during the 6 weeks of treatment), will be calculated using two-way ANOVA for repeated measures. Furthermore, the significant effect size of the comparison is calculated according to Cohen's effects (small (0.20), moderate (0.50) and large (0.80)).

o To identify the changes in the electromyographic activity of the multifractal analysis (Hurts Index and RMS) recorded by time of the right and left masseter muscles of all subjects, since each subject will be evaluated in 6 instances weekly, multilevel models will be adjusted (56) to describe the effect of the passage of time (T0 = Baseline, T1 = 7 days, T2 = 14 days, T3 = 21 days, T4 = 28 days, T5 = 35 days,

T6 = 42 days) of splint use and electrostimulation therapy and the effect of different explanatory variables on this change as on the initial value.

o All statistical calculations will be carried out in Stata 14 software (StataCorp., 2015).

Organization

a) Human resources

Tutor: [name] [name]

Tutorial Committee: Dra. [name] and [name] [name]

Operator: Mtra. [name]

External advisors: [name] and [name] [name]

b) Material resources:

EQUIPOS	INSTRUMENTAL	MATERIAL	STATIONERY
(1) Unidad odontológica	(10) Diagnostic equipment (mirror, caliper, scanner)	(50) (25 packs) Kendall® Electrodes	(50) Medical record formats -
(1) Electroestimulador de presión "Baseline" (1)	(3) Therbite	(50) (10 packs) Acupoint® needles	Laboratory of Physiology
Electromiógrafo digital CINVESTAV-UNAM	(2) Algometer	0.025mm x 25mm	(50) Informed consent forms
(1) Electroestimulador KWD-808	(100) Slay Tongues	(65) (2 boxes) Manhole covers	(50) Data collection sheets
(1) Computadora		(4 boxes) Gloves (5) Aerosol disinfectant	
(1) Impresora		(3 packs) Gauze	
(1) Cámara fotográfica		(1) Alcohol	
		(2 packs) Cotton	

c) Research development stages:

I. Training stage:

During the first, a review of the literature will be carried out and the methods of applying the therapies will be described.

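### Ha1 predicts that percutaneous stimulation beats both other arms, but the named between-group test is an omnibus ANOVA and no signed contrast is tied to Ha1

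*Protocol*

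**What the plan says.** **Hypothesis section.** Ha1 states for GB: "There will be a greater decrease in neuromuscular electrical activity (RMS) and muscle fatigue (Hurst index) of the masseter muscles", "compared to the values of the electrostimulation groups transcutaneous (GA = transcutaneous electrostimulation and splint) and the control group (CG = Occlusal splint". It therefore has a direction and two comparators.

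**Statistical data analysis plan.** Three statements bear on group differences:
- The muscle effect within and between groups over time "will be calculated using two-way ANOVA for repeated measures".
- In addition, "the significant effect size of the comparison is calculated according to" Cohen's benchmarks of 0.20, 0.50 and 0.80. No pair of groups is named.
- For RMS and the Hurst index, "multilevel models will be adjusted (56) to describe the effect of the passage of time". The sentence goes on to cover splint use, electrostimulation therapy, and the effect of explanatory variables on change and on the initial value. No group contrast is named or linked to Ha1.

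**Number of records.** The same section bases the model on six evaluations ("since each subject will be evaluated in 6 instances weekly") but lists T0 to T6, which is seven times. The Specific objectives do the same ("by means of 6 electromyographic recordings scheduled weekly", followed by T0 to T6). The recording technique says "6 electromyographic recordings will be performed on each patient (one record each week").

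**Sample size calculation.** It rests on a one-way ANOVA across three groups: 75.46 in total, 25 per group, raised to 28 per group (84) for losses.

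**The concern.** Ha1 holds only if GB does better than GA and also better than GC. The group and group-by-time F tests ask whether the three groups differ in any way. They can be significant because GA alone is worse, with GB and GC the same, and then Ha1 is false.

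Looking at the group means afterwards only partly helps. If GB and GC are truly equal, one of them will have the larger observed decrease by chance, and in about half of such trials it will be GB. With no contrast, time point or decision rule linked to Ha1, the choice of what counts as support would be made after the data are seen. At stake is a claim that percutaneous stimulation adds to the splint when the data show only that transcutaneous stimulation differs.

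**Working it through.** **1. The protocol's own ANOVA table.** Inputs: means 90.205 (transcutaneous), 79.99 (percutaneous) and 81.27 (control), 4 values per group, mean square within 74.2155.
- Grand mean = (360.82 + 319.96 + 325.08)/12 = 83.822.
- Between-group sum of squares = 4 × (6.383² + 3.832² + 2.552²) = 247.76, as printed.
- F = (247.76/2)/74.2155 = 1.669, as printed (p = 0.24).

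**2. What that F responds to.** Split the sum of squares into two orthogonal parts:
- Transcutaneous against the mean of the other two: difference 90.205 − 80.63 = 9.575; SS = 4 × 9.575²/1.5 = 244.48, or 98.7%.
- Percutaneous against control: difference −1.28; SS = 4 × 1.28²/2 = 3.28, or 1.3%.

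So an F on this pattern is almost wholly about GA. This is illustration only: with four trapezius values per group and p = 0.24, no true effect is established.

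**3. How often F would point to GB when only GA differs.** Assumptions: SD = √74.2155 = 8.61 µV, times T0 to T6, effect building up linearly, equal correlation between times of 0.5 or 0.7, 28 per arm, RMS only. The simulated rejection rates of the group-by-time F were:

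| Only GA higher by | correlation 0.5 | correlation 0.7 |
|---|---|---|
| 6 µV | 0.684 | 0.918 |
| 8.935 µV (90.205 − 81.27) | 0.982 | 1.000 |

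GB and GC are exchangeable here, so by symmetry GB has the larger observed decrease of the two in half of the significant trials, and GA is almost never the best. Half of each rate is 0.34, 0.46, 0.49 and 0.50: about 35–50%.

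**4. The two-contrast rule in the same settings.** GB minus GC is truly zero. The chance that it is significant in GB's favour at two-sided 0.05 is 0.05/2 = 2.5%, and the chance that both contrasts are cannot exceed that. The simulated rates (ANCOVA at the last time) were 2.0–2.6%. With six records (T0 to T5) and GA 8.935 µV higher, F rejects in 97–100% and both contrasts in 2–3%.

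**5. Power of the two-contrast rule on the planning means.** GB minus GC = −1.28 µV is the limiting contrast. Its standard error is √(2 × 74.2155 × v/n), with v = 1 − ρ² for ANCOVA and v = 2(1 − ρ) for change from T0. At n = 28, with power ≈ Φ(1.28/SE − 1.96):
- ANCOVA, ρ = 0.5: SE 1.99, Φ(−1.32) ≈ 9%. ρ = 0.7: SE 1.64, Φ(−1.18) ≈ 12%.
- Change from T0, ρ = 0.5: SE 2.30, Φ(−1.40) ≈ 8%. ρ = 0.7: SE 1.78, Φ(−1.24) ≈ 11%.

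The fuller ANCOVA calculation for both contrasts together gave 9–12% at 28 per arm and 8–11% at 25.

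**6. Gap needed for about 80% power (ANCOVA).** At 28 per arm GB must be about 6.5 µV (ρ = 0.5) or 5.25 µV (ρ = 0.7) below both other groups. At 25 per arm the gap is about 6.75 or 5.75 µV.

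**The case against.** **Contrasts belong in the SAP.** Follow-up comparisons, sidedness and decision rules are often left to an SAP, and an omnibus test followed by pairwise comparisons is routine with three arms. This stands as far as it goes: the absence of post-hoc detail alone would be no finding. But the protocol has its own statistical analysis section, and the between-group test named there does not answer the hypothesis that the protocol states.

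**The plan never says that a significant F supports Ha1.** This is correct. A reader might infer that the rule is F alone, and so a false claim in nearly every trial where only GA differs (98–100% at 8.9 µV). The text does not support that; those figures are the ordinary power of F. A reader might likewise infer that GB doing worse would count as success. F does reject in 68–92% when GB is 6 µV worse than both, but once the group means are read GB is credited in 0%. The GA-only case is not removed in this way, which is why the point rests on it.

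**The multilevel model already covers therapy.** It does, and could supply the signed differences. Cohen's benchmarks also suit pairs of means. Neither is linked to Ha1, and an effect size is not a test.

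**The numbers are thin.** The SD comes from four trapezius values per group with variances from 24.8 to 168.6, and only RMS was simulated. This stands for the exact percentages. The contrast between half the F rejection rate and a ceiling of 2.5% does not depend on the SD.

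**Conclusion.** The concern holds as a mismatch between a directional hypothesis with two comparators and a named between-group test that has no direction and does not single out GB. Even when read with the group means, a significant F would appear to favour GB in about 35–50% of trials in which only GA differs, against 2–3% under a rule that requires both contrasts. This assumes SD 8.6 µV, correlation 0.5–0.7, linear build-up, a GA difference of 6–8.9 µV and 28 per arm, and it is illustrative.

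It might also be inferred that the ANOVA is less powerful than the contrasts. That is not supported: with GB 6 µV better than both, the interaction F rejects in 67–92% and the two ANCOVA contrasts in 74–91%. The fault is what F tests, not its power. Severity is minor to moderate, because the protocol states no wrong decision rule and already plans a model that can answer Ha1.

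**What to change.** 1. Reconcile the six records with the seven listed times T0 to T6, because this decides which time is last.
2. Name one time point for Ha1 (the sponsor's choice).
3. Test Ha1 with two pre-specified signed contrasts, GB minus GA and GB minus GC, of change from T0 to that time. Take them as group-by-time contrasts from the planned multilevel model with T0 kept as an outcome. Alternatively, use an ANCOVA at that time with T0 as covariate. Do not do both: T0 should not be outcome and covariate in one model.
4. Declare Ha1 supported only if both contrasts favour GB at two-sided 0.05. Because both are required, no alpha split between them is needed. Keep the ANOVA as supportive.
5. State how RMS and the Hurst index combine in judging Ha1.
6. State in the sample-size section that 84 was sized for an omnibus ANOVA, and give the power of the two-contrast rule.

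The cost is analysis wording and a sentence on sample size, with no new visit or measurement. The downside to disclose is the 8–12% power on the planning means (ANCOVA version). Under the stated assumptions, unadjusted change contrasts have a standard error larger by √(1.0/0.75) = 1.15 at correlation 0.5 and √(0.6/0.51) = 1.08 at 0.7, so the ANCOVA version needs the smaller gap.
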